4.5. NIVOLUMAB DOSE MODIFICATIONS

Study Number: MCC 19178

Note: nivolumab dose should not be modified for toxicity.

When the medications need to be held for toxicity reasons, both cetuximab and nivolumab are always held together and restart together.

In cases where the treating physician delays treatment for symptoms not specified in this protocol, if such delays are documented as having been instituted in the patient's best interest this will not constitute a protocol deviation. If a patient is unavailable due to hospitalization, this too will not be considered a deviation from the protocol.

Nivolumab will be held for drug-related toxicities and severe life-threatening AEs as per Table 2 below. Held doses will not be replaced. When nivolumab is restarted, resume treatment along the anticipated schedule (i.e. doses are skipped rather than held). In the event of a treatment delay, the radiologic assessments will likewise be delayed so that restaging scans coincide with the start of the cycles specified in the study calendar.

Participants with adverse toxicity or persistent laboratory AE at grade 2 following 12 weeks of therapy may continue on the trial only if asymptomatic, controlled, and with the agreement of the principal investigator.

Table 2. Modification Guidelines for Nivolumab Drug-Related Adverse Events

Toxicity	Hold Treatment For	Timing For	Discontinue
	Grade	Restarting	Nivolumab
		Treatment	

AST, ALT, or	2	Toxicity resolves to	Toxicity does not
Increased Bilirubin		grade 0-1	resolve within 12
	3-4 ¹	Dormanontly	weeks of last dose Permanently
	3-4	Permanently discontinue (see	discontinue
		exceptions below)	discontinue
Diarrhea/Colitis	2-3	Toxicity resolves to	Toxicity does not
		grade 0-1	resolve within 12
			weeks of last dose
			or inability to reduce
			corticosteroid to 10 mg of prednisone or
			equivalent per day
			within 12 weeks
	4	Permanently	Permanently
		discontinue	discontinue
Hyperthyroidism	3	Toxicity resolves to	Toxicity does not
		grade 0 -1	resolve within 12
			weeks of last dose
			or inability to reduce corticosteroid to 10
			mg of prednisone or
			equivalent per day
			within 12 weeks
	4	Permanently	Permanently
	1	discontinue	discontinue
Hypothyroidism	2-4	Therapy with nivolumab can be	Therapy with nivolumab can be
		continued while	continued while
		treatment for the	thyroid replacement
		thyroid disorder is	is instituted
		instituted	
Hypophysitis	2-3	Toxicity resolves to	Toxicity does not
		grade 0-1. Therapy	resolve within 12
		with nivolumab can be continued while	weeks of last dose or inability to reduce
		endocrine	corticosteroid to 10
		replacement therapy	mg of prednisone or
		is instituted	equivalent per day
			within 12 weeks
	4		Permanently
Infusion Reaction	22	Toxicity resolves to	discontinue
IIIIUSIOII REACTIOII	Z-	Grade 0-1	Permanently discontinue if toxicity
			develops despite
			adequate
			premedication
	3–4	Permanently	Permanently
Dm		discontinue	discontinue
Pneumonitis	2	Toxicity resolves to	Toxicity does not resolve within 12
		grade 0-1	weeks of last dose
			or inability to reduce
			corticosteroid to 10
	L	L	continuositationa to 10

discontinue

			mg of prednisone or equivalent per day within 12 weeks
	3-4	Permanently discontinue	Permanently discontinue
Renal Failure or Nephritis	2	Toxicity resolves to grade 0 -1	Toxicity does not resolve within 12 weeks of last dose or inability to reduce corticosteroid to 10 mg of prednisone or equivalent per day within 12 weeks
	3-4	Permanently discontinue	Permanently discontinue
All Other Drug- Related Toxicities ³ .	3	Toxicity resolves to grade 0 -1	Toxicity does not resolve within 12 weeks of last dose or inability to reduce corticosteroid to 10 mg of prednisone or equivalent per day within 12 weeks
	4	Permanently	Permanently

IND#: Exempt

Note: Permanently discontinue for any severe or Grade 3 drug-related AE that recurs or any life-threatening event.

1. For patients with liver metastasis and who begin treatment with Grade 2 AST or ALT, if AST or ALT increases by greater than or equal to 50% relative to baseline and lasts for at least 1 week, then patient should be discontinued.

discontinue

- 2. If symptoms are resolved within one hour of stopping drug infusion, the infusion may be restarted at 50% of the original infusion rate for the next scheduled dose.
- 3. Patients with intolerable or persistent Grade 2 drug-related AE may hold study medication at physician's discretion. Study drug should be permanently discontinued for persistent Grade 2 adverse reactions for which treatment with nivolumab has been held that do not recover to Grade 0-1 within 12 weeks of the last dose.

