4.2.3. Definition of Dose-Limiting Toxicity of Cetuximab and Nivolumab

The phase I of the study will enroll 3 to 6 patients per dose level using a standard 3+3 design. The DLT period will start on Cycle 1 Day 1 of cetuximab and nivolumab and end on Cycle 1 Day 28. The toxicity after the lead-in cetuximab (Day -14 before Cycle 1 only) prior to the dosing of cetuximab and nivolumab will not be included to the assessment of DLT (Day -14 to Day -1).

The MTD will be determined using the following de-escalation rules:

- A cohort of three patients will be entered at Dose Level 1.
- If none of these patients experiences a DLT (see below for the criteria) during Cycle 1 (4 weeks), Dose Level 1 will be the recommended dose for Phase II.
- If 1 of these 3 patients experiences a DLT, 3 more patients will be enrolled at Dose Level 1. If 1 of 6 patients at this dose level experiences a DLT, the phase II dose will be Dose Level 1. If 2 or more DLTs occur within Dose Level 1, then the MTD will have been exceeded, and 6 new patients will be enrolled at Dose Level -1.
- If ≤1 of 6 patients at Dose Level -1 experiences a DLT, the phase II dose will be Dose Level -1. If 2 or more DLTs occur within Dose Level -1, then the MTD will have been exceeded. This combination is determined to be unsafe to conduct the phase II portion of the trial and the trial will be discontinued.

The target DLT rate is <25%. The MTD will be defined as the dose of cetuximab and nivolumab in which <1 of 3 patients experience a DLT or <2 of 6 patients experience a DLT with the next higher dose having at least 2 patients experiencing a DLT. The MTD is the highest dose at which at most 1 of 6 patients has a DLT.

IND#: Exempt

No dose escalations or de-escalations are permitted within each patient's treatment, although dose delays will be permitted. A patient who is withdrawn from the study before the completion of Cycle 1 for a reason other than a DLT will be replaced.

This study will utilize the Cancer Therapy Evaluation Program Common Terminology Criteria for Adverse Events (CTCAE) version 4.1 for toxicity and event reporting. DLTs will be observed until patients have completed Cycle 1 (4 weeks).

A DLT will be defined as any of the following events:

- Grade 3 or 4 immune-related toxicities, including dermatitis, hepatitis, thyroiditis, colitis, and pneumonitis.
- Grade 4 cetuximab-related rash.

Study Number: MCC 19178

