The median and 1-year progression-free survival rates will be estimated from the Kaplan-Meier curve with its 95% confidence interval.

• To evaluate the toxicity of the cetuximab and nivolumab combination in this patient population.

The toxicity data will be provided in a table by major toxicity category and for the highest toxicity grade for the patient.

Exploratory Objectives:

 To identify potential biomarkers related to response to concurrent cetuximab and nivolumab in patients with recurrent and/or metastatic HNSCC.

Exploratory analysis to assess the association of potential biomarkers with disease response will be made using logistic regression.

 To determine a quantitative radiomics based on CT and/or PET images as a prognostic biomarker in recurrent or metastatic HNSCC

Exploratory analysis to assess the association of potential radiomics signatures with disease response will be made using logistic regression.

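### Section 4.5 both fixes and moves the calendar after a treatment hold, so restaging dates, and with them recorded progression, can depend on treatment interruptions

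*Combined protocol and SAP*

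**What the plan says.** Section 4.5 opens by linking the two drugs: "both cetuximab and nivolumab are always held together and restart together". It then says "Nivolumab will be held for drug-related toxicities and severe life-threatening AEs as per Table 2 below" and that held doses are not replaced. On restart, sites are to "resume treatment along the anticipated schedule (i.e. doses are skipped rather than held". The next sentence reads "In the event of a treatment delay, the radiologic assessments will likewise be delayed", with the stated aim that scans line up with the cycle starts named in the study calendar.

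The same section allows other interruptions ("In cases where the treating physician delays treatment for symptoms not specified in this protocol") and mentions hospitalization. Section 4.2.3 states "No dose escalations or de-escalations are permitted within each patient's treatment, although dose delays will be permitted". Section 4.6.2 withholds both drugs around palliative radiotherapy. Section 3.3.4 ends protocol treatment once an interruption exceeds 12 consecutive weeks, whereas Table 2 counts 12 weeks from the last dose.

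Study calendar note n gives the scan schedule both in intervals and as named cycle visits; Section 4.2.4 gives it in weeks. PFS is a secondary endpoint. Section 10.1.2 says: "The median and 1-year progression-free survival rates will be estimated from the Kaplan-Meier curve". That section has no rule for late or off-schedule scans and no sensitivity analysis for them.

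**The concern.** If doses are skipped and treatment rejoins the original schedule, the cycle clock never stops and scans have no reason to move. If scans move so as to meet cycle starts, the cycle clock must have stopped. The word likewise comes directly after the hold rule, so a reader will take the scan sentence to cover toxicity holds. Two sites could scan the same patient on different dates and both could say they followed Section 4.5.

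Progression is dated largely by scan. Under the scan sentence, patients whose treatment is interrupted are imaged less often around the interruption than patients who tolerate treatment. The cohorts are single-arm, so no control group shares the shift. What is at stake is a secondary endpoint, the timing of recorded response, and how soon progression is seen in patients who are off drug.

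**Working it through.** **1. The protocol's own scan dates.** Inputs are the visits in study calendar note n and the 4-week cycle (Section 3.1). Week from C1D1 = ((cycle − 1) × 28 + (day − 1)) / 7.

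- C2D15: (28 + 14)/7 = 6
- C4D1: 84/7 = 12
- C6D1: 140/7 = 20
- C9D1: 224/7 = 32
- C12D1: 308/7 = 44
- C15D1: 392/7 = 56, and so on to C24D1: 644/7 = 92

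The gaps are 6, 6, 8, 12, 12, ... weeks, which reproduces the stated intervals. C2D15 is not the start of a cycle, so the scan sentence does not fit the first scan even on its own terms.

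**2. One patient, two calendars.** Take a 4-week hold starting in week 10, as an illustration. With doses skipped, scans fall at weeks 6, 12, 20, 32, 44. With scans delayed, they fall at weeks 6, 16, 24, 36, 48.

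**3. Gap length.** Under the scan sentence, a hold of h weeks turns a gap g into g + h.

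| Planned gap (weeks) | h = 4 | h = 12 |
|---|---|---|
| 6 | 10 | 18 |
| 8 | 12 | 20 |
| 12 | 16 | 24 |

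The 24 assumes that a full 12 weeks is counted from the first missed dose. If the 12 weeks run from the last dose, as in Table 2, two-weekly dosing means the calendar moves 12 − 2 = 10 weeks and the gap is 12 + 10 = 22.

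**4. Average delay in recording progression.** The documents give no hold rates, so these are simulations on assumed values, with exponential progression times and one hold per affected patient.

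- First set: 30 to 50% of patients assigned a hold of 4, 8 or 12 weeks, starting uniformly in weeks 2 to 40 and counted only if it starts before progression; true median 13 to 35 weeks. Mean recorded progression time rises by up to about 0.5 weeks over the cohort and about 2.6 weeks in held patients.
- Second set: 20 to 40% held for 4 or 12 weeks, starting in the first 12 weeks whether or not progression has already occurred; true median 13 to 26 weeks. The cohort mean rises by about 0.05 to 1.3 weeks. The largest case (median 13, 40% held, 12 weeks) is 24.56 − 23.27 = 1.29 weeks, or 1.29/0.40 ≈ 3.2 weeks per held patient.

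These are averages. In the step 2 example, a progression at week 11 is recorded at week 16 instead of 12, but one at week 33 is recorded at week 36 instead of 44.

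**5. One-year PFS.** On the fixed calendar there is no scan between weeks 44 and 56, so recorded 1-year PFS is S(44), not S(52). With S(t) = 2^(−t/m) for median m:

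| m (weeks) | True S(52) | Fixed calendar S(44) | Excess (points) |
|---|---|---|---|
| 13 | 6.3% | 9.6% | 3.3 |
| 26 | 25.0% | 30.9% | 5.9 |
| 35 | 35.7% | 41.8% | 6.1 |

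An earlier 4-week hold puts scans at weeks 48 and 60, so held patients contribute S(48), which is 27.8% at m = 26. An earlier 8-week hold puts a scan at week 52, giving S(52) = 25.0%. Both are nearer the truth than the fixed calendar. A 12-week hold starting before week 32 again leaves scans at weeks 44 and 56, so nothing changes; one starting between weeks 32 and 44 leaves no scan from week 32 to week 56, which is worse. Over the cohort, the first set of assumptions moves 1-year PFS by −3.0 to +0.8 points and the second by 0 to −1.2 points. The recorded median moves between scan dates in either direction.

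**6. Sampling error.** The approximate 95% half-width, ignoring censoring, is 1.96 × √(p(1 − p)/n). For p = 0.10 and n = 45 it is 8.8 points; for p = 0.36 and n = 43 it is 14.3 points.

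**The case against.** The strongest reply is that the two halves of the concern undercut each other. If doses are skipped, a toxicity hold does not move the calendar, scans need not move, and the link to toxicity largely disappears. Section 4.5 also tends to use held for Table 2 toxicities and delays for discretionary interruptions, so a reader could assign one sentence to each. That reading is possible, but the text neither defines the terms apart nor limits the scan sentence to one of them. The ambiguity stands; the dependence on toxicity holds only where the scan sentence is followed.

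The second reply concerns size, and most of it stands. The longest gap is a worst case: discretionary pauses for prolonged grade 2 toxicity are limited to 4 weeks (Sections 4.4.1 and 4.4.2), and scans may be done up to 7 days early. Tumor assessment by physical examination on Day 1 of each cycle (Section 4.2.4) and an end-of-treatment scan when none was done in the previous 4 weeks (calendar note o) give some other chance of detection.

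A reader might infer that the scan sentence inflates PFS and that a fixed calendar would make 1-year PFS more accurate. The protocol's own schedule does not support this. Step 5 shows that the 12-week grid overstates 1-year PFS by about 3 to 6 points by itself, and that 4- and 8-week shifts happen to bring a scan closer to week 52. Under the first set of assumptions the shifted calendar was nearer the truth for every 4- and 8-week scenario and further away, by under 1 point, only for 12-week holds.

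**Conclusion.** The contradiction in Section 4.5 is real and nothing elsewhere in the document resolves it. If the scan sentence is followed, imaging intervals depend on treatment interruptions: mainly toxicity, but also physician discretion, hospitalization and palliative radiotherapy. Progression is then recorded later on average in interrupted patients.

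The size is modest. One interruption stretches a 12-week gap to at most about 22 to 24 weeks. The average delay is up to about 2.6 weeks in interrupted patients and 0.5 weeks over the cohort under the first set of assumptions, and up to about 3.2 and 1.3 weeks with early holds. All of these rest on assumed hold frequency, length and timing and on exponential progression. The change in median and 1-year PFS has no fixed direction and is smaller than the 9 to 14 point half-width expected with 43 to 45 patients.

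It would be a mistake to carry this over to the main result. The primary endpoint is overall survival, which does not depend on scan dates, and neither do the sample sizes. This is a minor point, worth correcting because the calendar should be unambiguous and the same for every patient.

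**What to change.** State that restaging scans stay at calendar weeks from C1D1 (6, 12, 20, 32, then every 12 weeks) whether or not doses are given. These are the protocol's own visit dates, so no new schedule is imposed.

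Make matching edits where scans are tied to treatment visits or cycles: study calendar notes j and n and Section 4.2.4. Section 3.2.1 should be aligned at the same time, since it applies the 6-week interval to cycles 1 to 3 where the other two places say 1 to 4. Reconcile the skipped-dose sentence in Section 4.5 with the delay sentence that follows it, and define hold and delay if they are meant to differ. How doses are handled after a hold is for the sponsor to settle. A short PFS sensitivity analysis for late scans, for example with interval-censored progression times, would be a useful addition to Section 10.1.2.

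The cost is several small text edits, not one, and a few scans in weeks without a dosing visit. The number of scans is about the same. The change gives a uniform calendar; it should not be presented as correcting 1-year PFS, because the 12-week grid remains.

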4.5.1. Supportive Care Guidelines for Nivolumab

See also dose modification Section 4.5 and Table 2.

Immuno-oncology agents are associated with AEs that can differ in severity and duration than AEs caused by other therapeutic classes. Nivolumab is considered an immune-oncology agent in this protocol. Early recognition and management of AEs associated with immuno-oncology agents may mitigate severe toxicity. Management Algorithms have been developed to assist investigators in assessing and managing the following groups of AEs:

Gastrointestinal

Study Number: MCC 19178

- Renal
- Pulmonary
- Hepatic
- Endocrinopathy
- Skin
- Neurological

The above algorithms can be found in Appendix 4

4.5.1.1. Infusion Reaction (Nivolumab)

Study Number: MCC 19178

4.5.1.1.1 Hypersensitivity infusion reactions should be reported to the sponsor within 24 hours of the event regardless of grade. The following AE terms constitute hypersensitivity infusion reactions:

IND#: Exempt

- Allergic reaction
- Anaphylaxis
- · Cytokine release syndrome
- Serum sickness
- Infusion reactions
- Infusion-like reactions

4.5.1.1.2 Management of infusion reactions.

Infusion reaction treatment guidelines are summarized in Table 3 below. Institutional standards for infusion reactions may be followed if the treating physician deems them acceptable for this protocol.

Table 3. Management of infusion reaction

Grade 1 Mild reaction	Increase monitoring of vital signs as medically indicated until the patient is deemed medically stable in the	None
	opinion of the investigator	
Grade 2 Requires infusion interruption but responds promptly to symptomatic treatment (i.e., antihistamines, NSAIDS, narcotics, IV fluids); prophylactic medications indicated for ≤ 24 hours	Stop infusion and monitor symptoms. Additional appropriate medical therapy may include but is not limited to: IV fluids Antihistamines NSAIDS Acetaminophen Narcotics Increase monitoring of vital signs as medically indicated until the patient is deemed medically stable in the opinion of the investigator. If symptoms resolve within one hour of stopping drug infusion, the infusion may be restarted at 50% of the original infusion rate. Otherwise, dosing will be held until symptoms resolve, and the patient should be premedicated for the next scheduled dose. Patients who develop Grade 2 toxicity despite adequate premedication should be permanently discontinued from further trial treatment administration.	Subject may be premedicated 1.5h (± 30 minutes) prior to infusion of nivolumab with: • Diphenhydramin e 50 mg PO (or equivalent dose of antihistamine) • Acetaminophen 500-1000 mg PO (or equivalent dose of antipyretic)
Grade 3 or 4 Grade 3: Prolonged (i.e., not rapidly responsive to symptomatic medications and/or brief interruption of infusion); recurrence of symptoms following initial improvement; hospitalization indicated for other	Stop infusion. Additional appropriate medical therapy may include but is not limited to: IV fluids Antihistamines NSAIDS Acetaminophen Narcotics Oxygen Pressors Corticosteroids Epinephrine Increase monitoring of vital signs as medically	No subsequent dosing

clinical sequelae	indicated until the patient is deemed medically stable in	
(e.g., renal	the opinion of the investigator.	
impairment,	Hospitalization may be indicated.	
pulmonary	Patient is permanently discontinued from further trial	
infiltrates)	treatment administration.	
Grade 4:		
Life-threatening;		
pressor or		
ventilatory support		
indicated		

IND#: Exempt

4.6 CONCOMITANT TREATMENTS

Study Number: MCC 19178

4.6.1 Steroids

Treatment with oral/IV corticosteroids (>10mg daily prednisone equivalent) is not allowed for non-immunological toxicities. Treatment with oral/IV corticosteroids (>10mg daily prednisone equivalent) for immunological toxicities is permitted as detailed in the dose modification sections.

Use of corticosteroids (≤ 10 mg daily prednisone equivalents) is allowed. Inhaled or topical steroids and adrenal replacement doses > 10 mg daily prednisone equivalents are permitted in the absence of active autoimmune disease.

4.6.2 Radiation

Palliative radiation therapy is allowed to non-target lesions at the discretion of the treating physician. As concurrent radiotherapy and nivolumab/cetuximab have not been formally evaluated, in cases where palliative radiotherapy is required for a tumor lesion, then nivolumab/cetuximab should be withheld for at least 1 week before, during, and 1 week after radiation. Subjects should be closely monitored for any potential toxicity during and after receiving radiotherapy,

5. DRUG FORMULATION AND PROCUREMENT

5.1. CETUXIMAB

5.1.1. Packaging, Labelling, and Storage

Please refer to the Investigators Brochure for detailed information. Medication numbers will be unique to each bottle and will be used for tracking purposes only.

5.1.2. Supply

Cetuximab is supplied in a 100 mg/50 mL or 200 mg/100 mL solution in a single use vial.

5.1.3. Storage Conditions

Cetuximab must be stored in accordance with the instructions on the label.

5.1.4. Drug Accountability

Study Number: MCC 19178 IND#: Exempt

Drug supplies, which will be provided by Lilly Oncology, will be kept in a secure, limited access storage area under the storage conditions. Where necessary, a temperature log must be maintained to make certain that the drug supplies are stored at the correct temperature.

The responsible person must maintain records of the product's delivery to the study site, the inventory at the site, the use by each patient, and the return to Lilly Oncology or alternative disposition of unused product(s).

These records will include dates, quantities, batch/serial numbers, expiry ("use by") dates, and the unique code numbers assigned to the investigational product(s) and study patients. The responsible person will maintain records that document adequately that the patients were provided the doses specified by the clinical study protocol and reconcile all investigational product(s) received from Lilly Oncology. The responsible person must verify that all unused or partially used drug supplies have been returned by the clinical study patient.

